## Recruitment

**Aim 1:** Participants will be surgeons and medical staff at each of the 4 sites. We will conduct separate focus groups with surgeons and with the rest of the medical staff. Trauma chiefs (Co-Is on this grant) will not be included in the focus groups to avoid bias. The site PI and surgeon champion at each site, with support from the trauma chiefs will give presentations during the staff meetings to discuss the aim of the study, present preliminary data, discuss potential benefits to patients, and encourage participation. The RA at each site will next assist with recruitment, consent, and scheduling focus groups.

**Aim 2:** Participants will be recruited from each of the 4 Level 1 Trauma Center sites: MGH, Kentucky, Dell and Vanderbilt following a recruitment protocol developed and individualized for each site, consistent with prior recommendations, and informed by aim 1. Potential participants will be identified through screening of the medical record by the RA (injury in the prior 1-2 months, consistent with our preliminary data). The RA will next notify the medical staff (medical assistant) who will alert the surgeons. The surgeon will do a “warm hand-off” and introduce the RA and the study to the participants at the end of the medical visit. The RA will assess for eligibility (per criteria above). All participants will sign a consent form in REDCap prior to study procedures. All forms of recruitment will be submitted for IBR approval prior to use. Participants who meet eligibility criteria will complete baseline questionnaires on an iPad or on paper in clinic. The RA will be available to answer any questions.

Eligible cases may also be identified by daily screening of Epic admission reports.

After the conclusion of the intervention, we will also solicit feedback from orthopedic trauma providers about their perceptions of the feasibility, acceptability, and appropriateness of the TOR study in their clinic. Participants will be surgeons and medical staff at each of the 4 sites. Site PIs and surgeon champions will distribute survey links via email to providers at their site. After reviewing a consent fact sheet, participants will be asked to complete a brief demographic questionnaire as well as a brief survey regarding their perceptions on the implementation of the TOR study in their clinic (11 items).

## IV. SUBJECT ENROLLMENT

**Aim 1:** Surgeons and medical staff at the original 3 sites will be asked to participate in focus groups. It is anticipated that focus groups will comprise the following participants: 4 surgeon attendings, 1 fellow, 2 residents, 2 medical assistants, 1 nurse, 2 front desk staff, and 4

administrative assistants (MGH); 5 surgeons attendings, 27 fellows, 8 medical assistants, 2 nurses, 4 front desk staff (Kentucky); 4 attendings, 8 fellows, 2 nurses, 4 medical assistant, 6 front desk staff, and 10 other staff (e.g., schedulers, orthopedic technicians) (Dell). We have the full support from the orthopedic leadership at each site for these activities.

For Aim 1, we will obtain verbal consent from the medical professionals who agree to participate in the focus group sessions. Prior to verbal consent, study staff will inform participants that the focus group discussions will be audio recorded, as these recordings will be utilized to inform implementation of our mind-body intervention. All participants will be ensured that participation is strictly voluntary and confidential, and that it does not affect their care at any of the Partners Healthcare institutions. In addition, we will inform the participants about the confidentiality measures that the research group will take during the process. Only members of the research team will have access to the data, and the recorded transcriptions will be de-identified as to not contain identifiable or confidential information. The verbal consent process will include pertinent information on study design, risks and benefits, and voluntary nature of the research and confidentiality. Due to the nature of this study and the minimum risk, we would like to waive the written documentation of informed consent. However, study staff will document verbal consent by retaining a list of names of the participants who verbally consented and participated in the focus group. The consent process will be executed in a manner consistent with the IRB approved protocol, and the most recent version of the IRB-approved protocol will be used. Participants will be encouraged to review the study fact sheet, in its entirety, before verbally consenting. Study staff will answer any questions that participants may have. Participants will be given a copy of the fact sheet.

If a participant meets all study criteria, the RA will meet with the participant in a private location following their clinic visit to describe the study in detail including the consent form. All patients will have the opportunity to ask questions and will be given time to consider whether or not to participate. Participants will be informed of the potential risks and benefits of participation, and information regarding who they can contact for further questions. They will also be informed that participation is voluntary, that they can refuse to answer any questions, and they can withdraw from the study at any time. They will be informed that refusal to participate in the study will in no way impact their medical care. All participants will sign a consent form electronically in REDCap prior to study procedures. Participants will sign on an iPad in the clinic, or participants will be given the option to sign the consent form at home prior to completing study procedures remotely. Consent will include provision of consent to receive once daily text reminders to complete home practice (if randomized to TOR) as well as once daily reminders to record skills practiced (if randomized to TOR). All forms of recruitment will be submitted for IRB approval prior to use. Participants who meet eligibility criteria and consent will complete baseline questionnaires on an iPad or on paper in a private location in the clinic. The RA will be available to answer any questions. A trained research assistant will assist with the grip test (for upper extremity injuries) or walk test (for lower extremity injuries). Next, they will be randomized to TOR or Minimally Enhanced Usual Care (MEUC) and will receive a patient manual (TOR) or booklet (MEUC). Participants in both TOR and MEUC will also be provided with access to a website that contains the information from the treatment manual (for TOR) or printed booklet (for MEUC) and be assisted in accessing this website from their preferred device and bookmarking the website (e.g., downloading as an app), as desired. For those randomized to TOR the RA will install the Zoom secure live video platform on the participants' smart phones. For those who prefer to use a laptop, desktop or iPad, the RA will email a link and schedule a call to assist with the set up. The RA will also download the study website with pre-recorded TOR skills onto the participants' phones in an app form to aid with skills consolidation/practice. If enrolled participants do not have reliable access to a smartphone or other device or internet, the RA will provide the participant with a smartphone and set up a short-term data plan to enable participation in the study. Finally, the RA will schedule the first individual virtual visit with the clinician.

For the provider feedback surveys, surgeons and medical staff at each of the 4 sites will be asked to participate. Up to 80 providers are expected to participate. Medical professionals who choose to participate will provide implied consent based on their review of a study fact sheet in REDCap. All potential participants will be provided with a study fact sheet as the first page of a REDCap survey. The study fact sheet provides detailed information on the methodology and purpose of the study and the potential benefits/ risks associated with participating. All participants will be ensured that participation is strictly voluntary and confidential. In addition, the study fact sheet will inform the participants about the confidentiality measures that the research group will take during the process. Only members of the research team will have access to the data, and data will be de-identified as to not contain identifiable or confidential information. The study fact sheet will include pertinent information on study design, risks and benefits, and voluntary nature of the research and confidentiality. Participants will be encouraged to review the study fact sheet in its entirety before continuing to complete the brief REDCap survey. The study fact sheet will also contain the names and numbers of members of study staff that participants can contact if they have additional questions

or concerns. Due to the nature of this study and the minimum risk, we would like to waive the written documentation of informed consent. The consent process will be executed in a manner consistent with the IRB approved protocol, and the most recent version of the IRB-approved protocol will be used.

## V. STUDY PROCEDURES

**Aim 1:** Participants will be surgeons and medical staff at the original 3 sites. Participants will provide verbal informed consent prior to participation. Participants will be informed their participation is voluntary and they are not obligated to answer any questions. Next, we will conduct separate focus groups with surgeons and with the rest of the medical staff. Trauma chiefs (Co-Is on this grant) will not be included in the focus groups to avoid bias. The site PI and surgeon champion at each site, with support from the trauma chiefs will give presentations during the staff meetings to discuss the aim of the study, present preliminary data, discuss potential benefits to patients, and encourage participation. The RA at each site will next assist with recruitment, consent, and scheduling focus groups. For MGH surgeons, ideal focus groups are at 6:30 am or 7:00 am. Each site will prioritize recruitment, and the number of focus groups will depend on ability to schedule participants at each site. Exit interviews will be administered immediately after.

**Aim 2:** We will conduct a 4-site feasibility RCT and recruit 180 participants total (60 at the parent site, 50 completers; 40 per child site, 33-34 completers).

Baseline and follow-up assessments will include measurements of grip strength (for upper extremity injuries) or a walking test (for lower extremity injuries), which measures the time required to travel 10 meters, self-report measures assessing the primary (pain intensity and disability), and secondary (depression, PTSD, pain catastrophizing and pain anxiety) variables, and demographic information. Patients will complete the following reliable and valid battery of questionnaires, which will take approximately 20 minutes to complete:

- Demographics: Age, gender, race/ethnicity, education, employment, income, marital status, current psychotropic/pain medication intake, comorbid medical conditions, history of depression or other mental health conditions.
- Clinical variables: Injury type, date, location, prior pain (all by self report).
- Pain: Numerical Rating Scale, requires the patient to rate their pain on a defined scale (11-point scale from 0 (no pain) to 10 (worst pain)).
- Pain: Use of analgesics; Concomitant treatment: Daily self-report log.
- Physical function self-report: PROMIS Physical Function assesses one's ability to carry out activities that require physical actions, ranging from self-care to social and work.
- Physical function self-report: Short Musculoskeletal Function Assessment assesses patient's function as well as how bothered they are by their injury.
- Emotional function: The Center for Epidemiologic Study of Depression measures self-reported symptoms of depression.

- Emotional function: The PTSD Checklist civilian version measures symptoms of PTS.
- Coping: Pain Catastrophizing Scale assesses hopelessness, helplessness and rumination about pain.
- Coping: Pain Anxiety Scale, short form assesses avoidance, fearful thinking, cognitive and somatic symptoms of anxiety.
- Coping: Measures of Current Status (MOCS) assesses ability to engage in a series of healthy coping skills (e.g., relaxation, social support, adaptive thinking).
- Credibility and Expectancy Scale
- Mindfulness: 15-item Five-Facet Mindfulness Questionnaire (FFMQ-15)
- Experiential Avoidance: Acceptance and Action Questionnaire (AAQ-2)

Subjects will complete these questionnaires in the clinic or if there is not enough time, a researcher will send the questionnaires via a secure REDCap link for participants to complete at their home. At the 4 week follow up (after the intervention), they will also complete the Client Satisfaction Questionnaire to assess satisfaction with intervention. Patients will complete these measures on line via REDCap either in the clinic or from home. The walk test will be performed near a wall and a researcher will accompany the subject for the duration of the test. The subject will be informed that they should use the wall or researcher for balance, if needed, and this will be recorded. The grip strength test is routinely performed by researchers as part of other research projects in the department. The protocol for training and safety to ensure the reliability of results will be followed for this study. The grip strength test and walk test will be optional and subjects can refuse participation. Subjects may experience minimal pain during these exercises. The researchers will check the subject's medical record for any potential restrictions in activity and discuss with the treating physician any concerns about safety. We expect that most of the healing would have already occurred because we will be enrolling subjects about 0-3 months post injury date. Subjects in wheelchairs will not participate in the walk test.

Next, following guidelines for psychosocial clinical trials, we plan for a 1:1 RCT comparing 2 arms: 1) TOR (delivered via Zoom) + MEUC and 2) MEUC. Patients will be randomized based on scores on Pain Catastrophizing (PCS) and Pain Anxiety (PASS). PCS and PASS were chosen for the randomization based on our prior work with this population, which showed that PCS was the strongest predictor of pain intensity and PASS of long term disability. This method of randomization (median split on PASS and PCS) was successful in our previous face to face RCT. We will stratify participants by site, using the randomization module in REDCap, which will be prepared using permuted blocks by the study statistician. Out of the 180 participants enrolled, 90 will be randomized to TOR and 90 to MEUC. Within the 60 participants at the parent site, 30 will be randomized to TOR and 30 to MEUC. Within each of the 40 participants at the child sites, 20 will be randomized to TOR and 20 to MEUC. We will report on our primary and secondary outcomes specifically for each site (separate by study site strata). There will be 3 assessment points for the intervention: 1) baseline (0-3 months post trauma and before the intervention), 2) first follow-up post intervention (4 weeks post baseline), 3) second follow-up post intervention (3 months post baseline).

TOR has been developed tested and found efficacious in improving disability, pain, mood and coping in patients with orthopedic trauma, and we are ready to test it via videoconferencing to improve access to care. TOR has 4 sessions, 45 minutes each. TOR is focused on 1) discussing

the rationale for treatment and conducting motivational interviewing, 2) cognitive restructuring of patients' negative thoughts/misconceptions, 3) teaching patients to elicit the relaxation response through breathing retraining, progressive muscle relaxation and guided imagery, 4) helping patient decrease avoidance and return to activities including the injured limb, 5) increasing resiliency and preventing relapse. In both groups, patients will receive usual medical care (e.g., pain medications, physical therapy, and meetings with surgeons, medical staff) as currently delivered by orthopedic surgeons. In addition, participants in the control group, will receive a booklet containing brief summarized information that reflects the active intervention topics including the trajectory of pain and recovery after orthopedic illness, the role of relaxation strategies to manage pain and the importance of returning to engagement in activities of daily living. Participants in the MEUC will also be provided with access to a website that contains the educational information from the printed booklet in electronic format and be assisted in accessing this website from their preferred device and bookmarking the website, as desired. Participants in MEUC who do not own a smart phone will not be provided with one as they can also access the educational information in printed form access to a website that contains the educational information from the printed booklet in electronic format. The randomization process will increase likelihood of comparability of the two groups on the main study variable pain catastrophizing. Clinical staff at MGH will deliver TOR to participants at all sites.

Participants randomized to TOR will undergo set-up for the live video intervention prior to leaving the clinic. This includes: 1) installing Zoom and teaching participants how to use it; 2) scheduling their 4 weekly intervention sessions with the clinician; 3) setting up EZ texting to receive reminders; and 4) installing the TOR web platform (with session content and guided exercises) as an app on their phones. Participants who do not own a smart phone will be given one, and the RA will set their phone up at the first visit. We will also provide study participants with a data plan for the duration of the study, or brainstorm ways to access free internet (e.g., library, friends' houses), if needed. Our study team has used these strategies in prior studies. The RA will also schedule the participant's first session of TOR and ensure the participant writes down the date and time of the first session.

In order to ensure that participants in the TOR program are familiar with Zoom, the psychologist will schedule a brief session to go over how the software works and prepare the participants for the intervention.

Participants randomized to TOR will also receive daily text reminders through Twilio to practice program skills as well as record their skills practice if they consent to receive text reminders.

For the provider feedback surveys, surgeons and medical staff at each of the 4 sites will be asked to participate. Up to 80 providers are expected to participate. Participants will provide implied informed consent prior to participation. After reviewing a consent fact sheet, participants will be asked to complete a brief demographic questionnaire as well as a brief survey regarding their perceptions on the implementation of the TOR study in their clinic (11 items). Site PIs and surgeon champions will distribute surveys to providers at their site. We have the full support from the orthopedic leadership at each site for these activities.

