## **IX. MONITORING AND QUALITY ASSURANCE**

Electronic information will be stored in REDCap (Research Electronic Data Capture), a free, secure, and HIPAA-compliant web-based application hosted by the Partners HealthCare Research Computing Enterprise Research Infrastructure & Services (ERIS) group (based at the PHS Needham corporate datacenter). Data will be stored on password protected computers that will be stored in secure locations at all times. Paper data files (with coded subject identification) will be stored in a locked filing cabinet. Only research staff will have access to these data locations.

A unique anonymous identifier will be assigned to each subject; subsequently, all data collected will be associated exclusively with this identifier. This includes all questionnaires administered over the course of the study, as well as home practice logs.

Data from this study will be stored for three years after the publication of all study results, at which time all paper data files will be shredded, and computer files will be deleted.

The following study staff will be blinded: 1) overall PI; 2) site PIs; 3) surgeon champions; 4) study statistician; 5) RA involved with any post and follow up self-report and objective assessments; 6) statistician who is performing blinded analyses.

To achieve RA blindness, treatment assignment will be done by randomization RA, who will not be directly involved in evaluation or data collection. Survey data collection will be conducted by another RA who will be blinded to participant treatment assignment. Participant self-report surveys will be implemented using secured online survey software, which will significantly limit the potential of the RA to introduce bias. The overall PI, site PIs and surgeon champions will not be involved in the group assignment or collection of data. Also analyses will be conducted when data are unlocked. The study statistician and statistician who perform blinding analysis will not have access to randomization algorithm key.

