The following study staff will not be blinded: 1) randomization RA (RA who will randomize participants after consent and baseline and give participants study materials consistent with their respective treatment arm, and problem solves in real time and potential tech issues for those in TOR); 2) study therapists/clinicians; 3) the statistician who will develop the randomization scheme. The unblinded staff will have no access to data and no involvement in data monitoring and analyses.

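### The plan assigns the randomisation list to a role it also declares blinded, and does not say whether pain catastrophizing and pain anxiety scores are strata

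*Combined protocol and SAP*

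**What the plan says.** All references are to the combined protocol and SAP.

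**Who prepares the list**
- Section V, Aim 2, describes allocation "using the randomization module in REDCap, which will be prepared using permuted blocks by the study statistician".
- Section IX lists six blinded roles. The study statistician is the fourth, and the statistician doing the blinded analyses is a separate sixth. It adds: "The study statistician and statistician who perform blinding analysis will not have access to randomization algorithm key".
- Section IX then lists three unblinded roles: the randomising research assistant ("RA who will randomize participants after consent and baseline and give participants study materials consistent with their respective treatment arm"), the study clinicians, and "the statistician who will develop the randomization scheme". It continues: "The unblinded staff will have no access to data and no involvement in data monitoring and analyses".

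**What the strata are**
- Section V: "Patients will be randomized based on scores on Pain Catastrophizing (PCS) and Pain Anxiety (PASS". It explains why these two scores were chosen and adds: "This method of randomization (median split on PASS and PCS) was successful in our previous face to face RCT".
- It then says "We will stratify participants by site", the only factor it describes that way. It gives planned splits of 90/90 overall, 30/30 at the parent site and 20/20 at each child site. It states no PCS or PASS cut-point for this trial.
- Later in section V, randomisation is credited with making the arms more alike on pain catastrophizing.

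**Analysis**
- Section VI, Aim 2, describes a trial not powered for efficacy, with descriptive reporting and exploratory between-group analyses. It names no adjustment variables.
- Section IX ties the timing of the analyses to the data being unlocked.

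**The concern.** Whoever prepares a permuted-block list has seen it. A role cannot both prepare the list and be without the key, so the statements in sections V and IX cannot all be true. At stake is whether the trial can truthfully report that its study statistician was blinded.

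The second issue is that the randomisation paragraph does not define one design. A reader cannot tell whether balance on PCS and PASS is built in or left to chance, and so cannot judge the comparability claim or know which variables the analysis should respect. The trial exists to test methodology for a later efficacy trial, so an unclear randomisation description may be carried forward into it.

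**Working it through.** **1. The roles.** There are two ways to read section V.
- The study statistician and the scheme developer are the same person. Then the blinded listing in section IX and its statement about the key are both false for that person.
- They are different people. Then the sentence in section V names the wrong one.

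On either reading one statement must change.

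**2. What the list reveals.** The list fixes the order of arms within each stratum. Linking it to patients also needs enrolment order and stratum. The research assistant randomises after consent and baseline, so dated consent or baseline records would give that order closely. The documents do not say whether the study statistician sees such dates; that is an assumption. The supportable statement is therefore that this role could reconstruct the assignments.

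**3. The plan's own counts.** 60 + 3 × 40 = 180 in total, and 30 + 3 × 20 = 90 per arm. Both reproduce.

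**4. The two readings of the strata.**
- Site only: 4 strata.
- Site × PCS half × PASS half: 4 × 2 × 2 = 16 strata, averaging 60/4 = 15 patients at the parent site and 40/4 = 10 at each child site.

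These are different designs. A simulation (4,000 trials per setting) assumed median splits, a correlation of 0.5 between the scores, and blocks of 2, 4 or 6; none of these values is in the documents.
- The difference between arms in the number of high-PCS patients averaged about 5 (95th percentile 13) with site-only strata.
- It averaged about 2 (95th percentile 4 to 6) with 16 strata.
- With 16 strata, incomplete blocks meant that all four site splits were exact in only about 9%, 4% and 2% of trials for blocks of 2, 4 and 6. Exact counts could then only be targets.

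A median split also needs a number in advance: the median of this trial's own sample is unknown while patients are still being randomised.

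**5. Cost of adjustment.**
- Completers (section II, Aim 2): 50 + 3 × 33 = 149 to 50 + 3 × 34 = 152, so about 150.
- Covariate degrees of freedom: 3 for site, 1 for PCS, 1 for PASS, giving p = 5.
- Variance factor from estimating them: (n − 3)/(n − p − 3) = 147/142 = 1.035.
- Break-even share of outcome variance explained: 1 − 142/147 = 5/147 = 0.034.
- If the covariates explain 10%, relative variance is 0.90 × 1.035 = 0.93. At 30% it is 0.70 × 1.035 = 0.72. The 10% and 30% are assumptions; the documents give no value.

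**The case against.** The strongest reply on roles is that this is loose naming. Section IX already provides an unblinded statistician for the scheme, and section V agrees with that if it means the same person under another title; only the blinded list then clashes. That is probably what was intended. It lowers the severity but does not settle who holds the list.

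On the strata, the sponsor can say that section V describes PCS and PASS as the basis of randomisation and that site is simply an added factor. That is a fair reading, and the comparability sentence supports it. It still leaves the two scores unnamed as strata and without cut-points.

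A reader might infer from the exact 30/30 and 20/20 splits that only site is a stratum. The documents do not support this. Section III says the investigators aim at recruiting 60 and 40 per site, so the halves are planning figures, and planning figures cannot show which strata were intended.

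A reader might also take the unlocked-data wording as permission to edit data after seeing results. It may only mean released for analysis, so it is treated here as a wording slip.

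**Conclusion.** Should fix. The role contradiction stands on the text with high confidence and needs no assumption. Its reach is up to 180 assignments open to reconstruction by one of six roles declared blinded. The harm is limited because a different blinded statistician is listed for the analysis and the between-group comparisons are exploratory.

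The unspecified role of PCS and PASS also stands on the text. The imbalance figures illustrate the difference between the two designs under the stated assumptions; they are not evidence of a fault in either.

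Stronger conclusions that a reader might draw do not follow. The documents do not show that the study statistician actually knows each patient's arm, or that the analysis is unblinded. No block size is stated, so nothing can be said about how predictable assignments are. The 1:1 ratio is not threatened and no sample-size figure changes.

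**What to change.** 1. **Section V, list preparation.** Replace the study statistician with the unblinded statistician of section IX. If the list already exists, record who prepared it. If that was the study statistician, correct section IX instead.

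2. **Section V, strata.** Choose one:
   - (A) State that site is the only stratum, and remove the PCS/PASS basis and the later sentence on comparability.
   - (B) Name PCS and PASS as strata, with numeric cut-points fixed before enrolment, and describe 90/90, 30/30 and 20/20 as targets. Choose the cut-points for this trial's entry scores. The earlier trial's medians are not in the documents and may not suit patients selected on these scores. The entry rule must be reconciled first: section III joins the PCS and PASS thresholds by or, section IV by and.

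   If the list already exists, describe the strata actually programmed and leave the list unchanged.

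3. **Section VI, Aim 2.** Under either option, state that the exploratory between-group comparisons adjust for site and baseline PCS and PASS.

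4. **Section IX, minor.** Say that analyses follow database lock.

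**Cost.** Items 1 and 4 and option A are wording. Option B changes how the REDCap module is built, so it is open only before the list is made. Item 3 uses data already collected and costs the 5 degrees of freedom shown above.

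### Device support for home follow-up is tied to arm and worded inconsistently, so completion of the online questionnaires may differ between TOR and MEUC

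*Combined protocol and SAP*

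**What the plan says.** Three statements in the combined protocol and SAP govern who gets a device.

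- **MEUC, in V. Study Procedures, Aim 2:** "Participants in MEUC who do not own a smart phone will not be provided with one". The reason given is that the educational information is also available in print.
- **TOR set-up, same section:** "Participants who do not own a smart phone will be given one, and the RA will set their phone up at the first visit". The next sentence is worded more broadly: "We will also provide study participants with a data plan for the duration of the study". It adds, as an alternative, helping people find free internet access.
- **IV. Subject Enrollment, Aim 2:** "If enrolled participants do not have reliable access to a smartphone or other device or internet, the RA will provide the participant with a smartphone". It goes on to promise a data plan, described there as short-term. No arm is named, although the neighbouring sentences concern TOR set-up.

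On outcome collection, V. Study Procedures says of the questionnaires: "Patients will complete these measures on line via REDCap either in the clinic or from home". The Recruitment text under III and section IV allow paper as well as an iPad, but only for the baseline questionnaires. Follow-up is at 4 weeks and 3 months after baseline.

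**The concern.** The reason for withholding phones from MEUC is sound for the intervention: a printed booklet needs no phone. It does not deal with how the same people return their follow-up data. A TOR participant who arrives without a device is equipped, by the set-up rule, to answer from home. A MEUC participant in the same position can answer only by coming to the clinic. I. Background and Significance describes that travel as a burden even for patients living nearby, because many cannot drive.

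The plan sets completer targets (II. Specific Aims and V. Study Procedures), and the trial exists to show whether the methods are fit for an efficacy trial. If completion is lower in MEUC, the investigators could not tell whether the control condition retains people poorly or whether some of them had no convenient way to answer. The people lost would also be a selected group, those without devices or internet. VI. Biostatistic Analysis states no method for missing data and does not list completion by arm among the quantities to be reported.

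**Working it through.** **1. What each arm has for follow-up, if the participant has no usable device or internet**

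- TOR: phone supplied, with a data plan or help finding internet access. Routes: home or clinic.
- MEUC under the rule in V: no phone, and no data plan clearly promised. Route: clinic.
- MEUC under the literal wording of IV: phone and data plan. Routes: home or clinic.

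The two MEUC lines cannot both apply. Four sites reading the same protocol could act differently.

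**2. The plan's own loss figure**

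- Parent site: 50/60 = 83.3% completers, a loss of 16.7%.
- Child sites: 33/40 = 82.5% to 34/40 = 85.0%, a loss of 15.0–17.5%. A loss of one sixth gives 40 × 5/6 = 33.3, which explains the range of 33–34.
- Total: 50 + 3 × 33 = 149 to 50 + 3 × 34 = 152 of 180, a loss of 31/180 = 17.2% to 28/180 = 15.6%.

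The stated counts reproduce at a loss of about one sixth. With 90 per arm and equal loss, that is 75 completers and 15 losses in each arm.

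**3. Illustrative gap in completion**

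The documents give neither the share without a device nor its effect on completion. Both are assumptions here, as is full equalisation of completion in TOR by the phone supplied.

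Gap = share without a device × drop in completion without one.

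- Low: 0.05 × 0.20 = 0.010, or 1.0 point (0.9 of 90 participants).
- Middle: 0.10 × 0.35 = 0.035, or 3.5 points (3.15 of 90).
- High: 0.15 × 0.50 = 0.075, or 7.5 points (6.75 of 90).

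Outcomes are to be reported by site, and a child site has 20 MEUC participants. There, one extra loss moves that arm's completion by 1/20 = 5 points.

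**4. Illustrative effect on a between-arm mean**

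Let s be the share without a device, and q the proportion of them lost among those who would otherwise have stayed. Their share among observed MEUC participants is s(1 − q)/(1 − sq). The shift in the available-case mean is the fall in that share times the amount by which they differ on the outcome.

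- With s = 0.10 and q = 0.5, the observed share is 0.05/0.95 = 0.0526. The fall is 0.10 − 0.0526 = 0.0474. If they differ by 0.3–0.5 SD, the shift is 0.0474 × 0.3 = 0.014 to 0.0474 × 0.5 = 0.024 SD.
- At an extreme outside the range in step 3 (s = 0.20, all lost, 0.5 SD), the shift is 0.20 × 0.5 = 0.10 SD.

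**5. Would a test of missingness reveal it?**

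With 90 per arm and a two-sided 5% test, the chance of detecting a loss of 20.8% against 16.7% is about 11%. For 25.0% against 16.7% it is about 28%. A non-significant comparison would not show that the access rule did no harm.

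**The case against.** The strongest reply is that the difference is deliberate and touches few people. TOR is delivered by live video and cannot be received without a device, whereas MEUC can be received on paper. Only a smartphone is withheld. A REDCap link can be opened on any device with internet, and MEUC participants are helped to reach their website on whatever device they prefer. In-clinic completion is open to both arms, and grip or walk tests are part of follow-up, so both arms are asked to attend in any case. TOR's advantage may not last to month 3 if the data plan is short-term, as section IV has it. Between-arm analyses are exploratory.

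Much of this stands. It limits the point to participants with no usable device or internet. A reader might infer that missing data will differ by arm; the documents support only that they may. The reply does not answer the core, because the grip and walk tests are optional, and the reason given for withholding phones never mentions outcome collection.

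A reader might also link the TOR-only daily texts to the analgesic measure, listed as "Use of analgesics; Concomitant treatment: Daily self-report log", and expect fuller logs in TOR. The documents do not support that. The texts are described thus: "Participants randomized to TOR will also receive daily text reminders through Twilio to practice program skills as well as record their skills practice". They prompt skills practice, not the analgesic log. The log's medium is not stated and may be paper. The questionnaire battery also asks about current pain medication.

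Finally, the sentence in section IV sits among TOR set-up instructions and was probably meant for TOR alone. If so, the conflict is one of wording, but it still needs correcting.

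**Conclusion.** The point holds in limited form. Home access for follow-up depends on arm for participants without a usable device or internet, for a reason that concerns the intervention content only, and the statements on devices and data plans do not agree. Loss to follow-up may differ by arm as a result.

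The size cannot be derived from the documents. On the assumed inputs the gap is 1.0–7.5 points, or roughly 1 to 7 of 90 MEUC participants, against planned loss of about 17%. This assumes that a supplied phone removes the disadvantage in TOR and that nothing else drives loss apart. The effect on exploratory mean differences is probably small. The main consequence is for reading completion by arm and by site as a feasibility result. The change is worth making because the cause is avoidable and the remedy cheap, not because a large bias has been shown.

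**What to change.** 1. Reconcile section IV and the two statements in section V: say which arm receives devices and data plans, for what purpose, and until which assessment. The short-term plan in IV and the study-long plan in V also need to agree.
2. Record device and internet access at baseline, before randomization. Offer everyone recorded as lacking access, in either arm, the same follow-up route that needs no device, for example the paper questionnaires already allowed at baseline, by post or at the clinic visit. Making the offer alike in both arms also keeps the paper form from signalling allocation to the blinded assessor.
3. Add to VI. Biostatistic Analysis a descriptive table of questionnaire completion at 4 weeks and 3 months by arm and baseline device access, without relying on a significance test.

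The cost is protocol wording, some paper packets and postage, and entry of the paper forms into REDCap. No phones for MEUC are needed, and the contrast between TOR and MEUC is unchanged.
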